Regarding the CRT AutoAdapt feature, the available clinical data show beneficial effects of continuous automatic, ambulatory CRT optimization over standard echo-guided optimization at implant. Ambulatory CRT optimization was associated with a higher proportion of patients receiving effective CRT, an improved Clinical Composite Score (CCS), a reduction in HF hospitalization, the reduced occurrence of AF and death. Since AdaptivCRT (aCRT, a competitive algorithm) and the functionally similar CRT AutoAdapt require intact AV node, right bundle conduction, and absence of atrial tachycardia, patients fulfilling these criteria were shown to benefit more than the overall collective patients with CRT indication. Furthermore, LV-only pacing, i.e. withholding right ventricular pacing when intrinsic electrical conduction to the right ventricle is normal, was shown to result in similar or superior LV function and was also associated with improved RV function vs. BiV pacing⁴³⁻⁴⁶. It was criticized that the entirety of findings regarding clinical outcomes of aCRT is based on only one prospective trial and associated retrospective subgroup analyses. However, based on available data, aCRT and most probably also CRT AutoAdapt offer clinicians and patients enhanced options to improve response to CRT.

The use of Home Monitoring functionality offers the physicians the possibility to monitor their patients remotely whenever it is deemed necessary. The automatic early detection of arrhythmia and device anomalies allows earlier medical intervention as compared to conventional in-office follow-ups. The results of the TRUST clinical study demonstrated the safety and effectiveness of the remote monitoring⁴⁷. In the Cor Family ICDs, the QuickCheck feature offers the additional advantage of providing a "real-time" report including a current periodic IEGM typically within 3-4 minutes of triggering it, e.g. if the patient experiences symptoms.

Finally, the new design of the Cor Family devices is expected to provide greater patient comfort and a better cosmetic outcome.

The individual benefit of study participation for the patient is an intensified medical supervision of his clinical status. In CRT-D patients the chance of responding to CRT-D therapy might be increased due to the increased number of LV pacing vectors, MultiPole Pacing and CRT AutoAdapt.

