9.1 Overview

Table 5 : Overview of study procedures. The exact reference time for the 3-, 6- and 12-month follow-up is defined as 92 days, 183 days and 365 days after implantation, respectively. The applicable time window is \pm 30 days around this reference time.

Investigations	Enroll- ment	Implan- tation	PHD	3- Month FU	6- Month FU	12- Month FU
Verification of in- and exclusion criteria	x					
Patient informed consent	x					
Documentation of demographic and health status data	x					
Documentation of cardiovascular medication	x	x	x	x	x	x
Documentation of indication for ICD/CRT-D therapy (incl. available diagnostics)	x					
ICD/CRT-D implantation		x				
Assessment of ICD/CRT-D shape		x				
Assessment of Plexa S DX Lead handling		x				
Assessment of Selectra catheter handling		x				
Record device based sensing, pacing threshold and impedance values		x	x	x	x	x
Evaluation of system performance		x	x	x	x	x
Evaluation of tachyarrhythmia episodes		x	x	x	x	x
Registration at HM Service Center, hand out CardioMessenger		(x)	x			
Home Monitoring 'ON'		x	x	x	x	(x)
Recording Episode IEGMs (event triggered): 'ON'		x	x	x	x	(x)
Automatic LV VectorOpt test		(x)	x	(x)		
CRT AutoAdapt 'ON' (Acticor/Rivacor 7 CRT-D)		(x)	x	(x)	(x)	(x)

Investigations	Enroll- ment	Implan- tation	PHD	3- Month FU	6- Month FU	12- Month FU
Evaluation of CRT Auto Adapt Feature (Acticor/ Rivacor 7 CRT-D)				x		(x) ⁴
AV Opt Test (VR-T DX/ DR-T/Rivacor 5 CRT-D)			x	(x)		
Documentation of Quick Check				x	x	x
Documentation of MPP settings (for HF-T QP)		x	x	x	x	x
Documentation of MRI examination			x	x	x	x
Assessment of patient's wearing comfort (in case of exchange)				x		
Evaluation of ATP statistics page						x
eCRF completion	x	x	x	x	x	x
Provision of programmer data via ReportShare		x	x	x	x	x
Adverse event and device deficiency reporting	x	x	x	x	x	x
Regular study termination						x

x=if applicable, (x)=optional

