15. Report all adverse events. In case of a serious adverse event, or adverse device effect (ADE), please provide the information immediately to BIOTRONIK, and inform the

ethical committee, if required. Report adverse events within the indicated timelines (see section 18.9).

9.5 3-month follow-up

Three months (92 ± 30 days) after the implant procedure, the patient has to return to the hospital for assessment of the implanted system. The investigator reviews the system performance and adjusts the programmed parameters as necessary to optimize the ICD/CRT functions. The requirements of this procedure are listed below:

1. Reprogram ICD settings as applicable to optimize ICD/CRT-D function
2. Perform device-based measurements of pacing thresholds and sensing amplitudes, pacing impedances and shock impedances via Renamic programmer (see 8.1.4.15)
3. Evaluate system performance (sensing and pacing)
4. Document and evaluate tachyarrhythmia episodes, if applicable (see 8.1.4.16)
5. Perform Automatic LV VectorOpt Test (if not yet done at implantation or PHD) for all CRT-D patients (mandatory, see 8.1.4.8)
6. Perform AV Opt Test (if not yet done at PHD) for all patients with VR-T DX or DR-T devices and for patients with Rivacor 5 triple-chamber devices (see 8.1.4.10)
7. Evaluate CRT AutoAdapt feature for CRT-D patients implanted with Acticor 7 or Rivacor 7 devices (see 8.1.4.9)
8. Program the following mandatory device settings:
 - Home Monitoring: 'ON'
 - Recording episode IEGMs (event-triggered): 'ON'
9. Program the following recommended device settings:
 - For patients implanted with Acticor 7 or Rivacor 7 devices: QuickCheck 'ON'
 - For patients implanted with VR-T DX devices: activate alert for 'detection of atrial monitoring episode' in HMSC
10. Document current medication on the medication log (see 8.1.4.21)
11. Document use of QuickCheck, if applicable (see 8.1.4.11)
12. For HF-T QP patients: Document MPP settings, if applicable (see 8.1.4.12)
13. Document MRI examinations since implantation, if applicable (see 8.1.4.14)
14. If the initial study implantation was a device exchange: ask the patient about their wearing comfort compared to the previous device
15. Complete the electronic Case Report Form (eCRF) in a timely manner
16. Provide programmer data (see 8.1.4.19)

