- Nominal values Original values from CDMS data will be used for generating the SAR unless new nominal values are defined in this document ("NEW"); values might be omitted or shortened ("...") if remaining clear; for numeric data this information is not applicable (n.a.)

Data file, unique identifier patient_display_id_full patient_display_id_full Patient display ID nominal	Notes ...	Variable name	Variable label	Variable level	Nominal values

2 Objectives

CIP chapter 7.1.Objectives

This study is designed as post market clinical follow-up study to identify and evaluate residual risks associated with the use of the Cor Family ICDs and the Plexa S DX lead that remained unrevealed even after risk analysis, risk mitigation and successful conformity assessment.

Moreover, the study aims at providing additional data, as required by regulatory authorities outside the CE-region. Furthermore, the performance and efficacy of the Cor Family devices and their features, as well as of the Plexa S DX lead shall be assessed. The results will be used for updating the clinical evaluation.

The primary objective of the clinical investigation is to confirm the clinical safety of the Cor Family ICDs by the analysis of the Cor Family-related SADEs until the 3-month follow-up.

Secondary objectives are the Kaplan-Meier estimate of the SADE-free rate at 3 and 12 months after implantation, the assessment of the automatic LV VectorOpt test, as well as the assessment of the CRT AutoAdapt feature.

3 Investigational Device

CIP chapter 4.1 Summary description of the device and its intended purpose

The investigational devices used in this clinical investigation are the ICDs and CRT-Ds of the Acticor/Rivacor ICD family and the Plexa ProMRI S DX ICD lead.

The ICDs/CRT-Ds of the Acticor/Rivacor family are state-of-the art implantable defibrillators intended for defibrillator therapy in patients with indication for primary or secondary prevention of sudden cardiac death. Triple-chamber devices (CRT-D) are additionally indicated for cardiac resynchronization therapy (CRT) for patients with congestive heart failure with ventricular asynchrony.

The Plexa ProMRI S DX ICD lead is intended for implantation in the right ventricle to deliver ATP and shock therapies during ventricular tachycardia. The lead provides sensing and pacing in the right ventricle, as well as sensing in the right atrium (floating atrial dipole).

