		betablocker	BL med: Betablocker (excluding sotalol)	nominal	 Yes  No
		ccblocker	BL med: Calcium channel blocker	nominal	 Yes  No
		digitalis	BL med: Digitalis	nominal	 Yes  No
		diuretics	BL med: Diuretics (other than Aldosterone blocker)	nominal	 Yes  No
		statins	BL med: Statins	nominal	 Yes  No
		other_cv_med	BL med: Other cardiovascular medication	nominal	 Yes  No
		non_cv_med	BL med: Non-cardiovascular medication	nominal	 Yes  No

Implantation / investigational device system

Data file, identifier patient_display_id_full	Notes	Variable name	Variable label	Variable level	Nominal values
implantation	descr.	PRIMTYP	Type of implantation	nominal	 De-novo system  Upgrade system  Device exchange
	descr.	PRIMRATY	Type of RA lead implantation	nominal	 New RA lead  Previously implanted RA lead  No RA lead implanted
	descr.	PRIMRVTY	Type of RV lead implantation	nominal	 New RV lead  Previously implanted RV lead  No RV lead implanted
	descr.	PRIMLVTY	Type of LV CS lead implantation	nominal	 New LV CS lead  Previously implanted LV lead  No attempt to implant LV CS lead  Unsuccessful attempt to implant LV CS lead  No LV lead implanted

Data file, identifier patient_display_id_full	Notes	Variable name	Variable label	Variable level	Nominal values
implantation	case listings for PRIMLVTY = No attempt to implant LV CS lead	PRLVCSRE	Reason for no attempt to implant LV CS lead	nominal	 Use of LV epicardial lead  Use of LV endocardial lead  Other
		COLVCSRE	Specification of other reason for no attempt to implant LV CS lead	text	n.a.

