8.2.2 Assessment of ICD/CRT-D design (size and shape)

CIP chapter 8.1.4.5 Assessment of ICD/CRT-D design (size and shape)

The implanting investigator will be asked to assess the new design of the Cor Family devices ... In case of device exchanges, the patient will be asked about their wearing comfort compared to their previous device at the 3-month follow-up.

Implantation/ Assessment of ICD/CRT-D design

Data file, identifier patient_display_id_full	Notes	Variable name	Variable label	Variable level	Ordinal values
implantation	descriptive	DXIMLAS_R	Required length of incision	nominal	 Very good  Good  Adequate  Poor  Very poor
	descriptive	DULDCAS	Lead connection		
	descriptive	DULDBAS	Lead body leading out of the header		

Data file, identifier patient_display_id_full	Notes	Variable name	Variable label	Variable level	Ordinal values
implantation	case listings	COIMLAS	Please specify required length of incision	text	n.a.
		COLDCAS	Please specify lead connection		
		COLDBAS	Please specify lead body leading out of the header		

Implantation/ Comparison of properties with BIOTRONIK's predecessor devices

Data file, identifier patient_display_id_full	Notes	Variable name	Variable label	Variable level	Nominal values
implantation	descr.	DIPRDV	Provide information on predecessor devices	nominal	 Lumax  Idova  Iforia  Ilesto  Ilivia  Inlexa  Intica  Inventra  Iperia  Itrevia  Other
	descr.	DUPCMKAS	Ease / time needed for making the pocket for predecessor		 Much more convenient  More convenient  Similar  Worse  Much worse
	descr.	DUSZPHAS	Assessment of size and shape for the patient's comfort for predecessor		 Much more convenient  More convenient  Similar  Worse  Much worse
	descr.	DUISPLAS01	Ease, securing, and placement for predecessor		 Much better  Better  Similar  Worse  Much worse

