	descr.	DUPHSHAS01	Interference for competitor	nominal	 Much less (most physiological)  Less (more physiological)  Similar  More (less physiological)  Much more (least physiological)

Data file, identifier patient_display_id_full	Notes	Variable name	Variable label	Variable level
implantation	case listings for DIDVMNF = Other	CODVMNF	Please provide name of "other" competitor	text
	case listings	COPCMKAS01	comment on ease/time needed for making the pocket for competitor	text
	case listings	COSZPHAS01	comment on assessment of size and shape for the patient's comfort for competitor	text
	case listings NOTE deviating index	COISPLAS02	comment on ease, securing, and placement for competitor	text
	case listings	COCSMTAS01	comment on cosmetic outcome for competitor	text
	case listings	COPHSHAS01	comment on interference for competitor	text

follow_up_3m / Wearing Comfort in case of Device Exchange

Data file, identifier patient_display_id_full	Notes	Variable name	Variable label	Variable level	Ordinal values
implantation	no report	PRIMTYP	Type of implantation	nominal	 De-novo system  Upgrade system
follow_up_3m	descriptive for PRIMTYP=Upgrade system	DUWCDVAS	How did the patient assess the wearing comfort of the device compared to its predecessor	nominal	 Much more convenient  More convenient  Similar  Worse  Much worse

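### SAP 8.2.2 filters the wearing-comfort table on upgrade patients, although the question is put to device-exchange patients; a few other descriptive entries in SAP 8.2 also need correcting

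*SAP*

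**What the plan says.** **Wearing comfort.** The table in SAP 8.2.2 is headed "Wearing Comfort in case of Device Exchange". The section opens by reproducing the protocol rule: "In case of device exchanges, the patient will be asked about their wearing comfort compared to their previous device at the 3-month follow-up". Protocol 8.1.4.5 is the source of that sentence. Protocol 9.5 item 14 gives the site instruction: "If the initial study implantation was a device exchange: ask the patient about their wearing comfort compared to the previous device". The schedule in Protocol 9.1, repeated in SAP chapter 4, carries the same restriction. The analysis note for the rating (`DUWCDVAS`) is nevertheless "descriptive for PRIMTYP=Upgrade system". In SAP 8.2.1 the type of implantation (`PRIMTYP`) has three levels: de novo, upgrade, and "Device exchange".

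**Right-ventricular (RV) performance.** In the RV table of SAP 8.2.5, the row for the reason for inadequate RV sensing carries `DURASARE`, and the row for adequate RV pacing carries `DURAPCAD`. Both names appear, with right-atrial (RA) labels, in the RA table of the same section.

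**Heart valves.** In the comorbidity table of SAP 8.2.1, the note on the valve block restricts the description to patients with `MHAOVA` = Yes. `MHAOVA` (aortic valve affected) is the first of the six valve items.

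**The concern.** A SAP filter is an instruction to the programmer. Here it selects a group that the protocol does not ask and leaves out the group that it does ask. Protocol 6.1 lists comfort among the expected benefits of the new housing ("Finally, the new design of the Cor Family devices is expected to provide greater patient comfort and a better cosmetic outcome"), and this is the item in which the patient answers directly. An empty or nearly empty table would lose that evidence although it had been collected.

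The RV rows matter because SAP 8.1 runs the sensing and pacing assessment separately for the Plexa lead set. That lead paces the right ventricle but only senses in the atrium. A row labelled as RV pacing but filled from an atrial pacing item would not describe the lead.

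The valve note would distort the baseline description of valve disease.

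**Working it through.** The plan gives no figure to reproduce. The check sets the entries side by side and counts.

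**1. Wearing comfort**

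| Place | Group |
|---|---|
| SAP 8.2.2, table heading | Device exchange |
| SAP 8.2.2, protocol excerpt | Device exchange |
| Protocol 8.1.4.5 | Device exchange |
| Protocol 9.5 item 14 | Device exchange |
| Protocol 9.1 schedule, repeated in SAP chapter 4 | Exchange |
| SAP 8.2.2, analysis note | Upgrade |

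Let *u* be the number of upgrade patients and *e* the number of exchange patients. `PRIMTYP` takes one value per patient, so the filter keeps *u* patients and 0 of the *e*. This holds for any *e*; the documents give neither number. Sites that follow Protocol 9.5 item 14 collect answers from the *e* only. The table would then show *u* patients with few or no answers, and the *e* answers would not be tabulated.

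The value list beside `PRIMTYP` in SAP 8.2.2 shows only de novo and upgrade. SAP 1.3 allows this ("values might be omitted or shortened"), so the shortened list is not the defect. The filter is.

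**2. RV table, SAP 8.2.5**

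| Item | RV table | Left-ventricular (LV) table |
|---|---|---|
| Sensing adequate | `DURVSAAD` | `DULVSAAD` |
| Reason, sensing | `DURASARE` (RA name) | `DULVSARE` |
| Pacing adequate | `DURAPCAD` (RA name) | `DULVPCAD` |
| Reason, pacing | `DURVPCRE` | `DULVPCRE` |

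RA names stand in 2 of 4 RV rows, against 0 of 4 in the parallel LV table. The RV case listing below the table uses `DURVSARE`, which confirms the intended name for the sensing reason. The intended name for pacing adequacy is not printed anywhere in the SAP; the pattern suggests `DURVPCAD`. Followed literally, RA results print under RV labels, and the RV sensing reasons and RV pacing-adequacy rate are not reported. RV sensing adequacy, the reasons for inadequate RV pacing, and RV thresholds and impedances are still reported.

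**3. Valve note, SAP 8.2.1**

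The six rows are `MHAOVA`, `MHMIVA`, `MHMINT`, `MHMIST`, `MHTRVA` and `MHPUVA`. Among patients with `MHAOVA` = Yes, the aortic rate is n(Yes) / n(Yes) = 100%. If the note also spans the other five rows, patients with isolated mitral, tricuspid or pulmonary disease drop out of those rows. Neighbouring notes filter a detail on its parent item: AV block type on `MHAVB`, sleep apnoea type on `MHSAP`. The parent here is `MHVHD`. That item and the free text `COVHD` are still reported without the filter.

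**4. Two clean-ups, no wrong result shown**

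- SAP 9.2.6 treats a `Not done` answer to `DURVLVAS` as missing. SAP 13.2 reports the same variable for secondary endpoint 2 without that note.
- In SAP 8.2.6, the four per-patient rows on shocks for VT episodes repeat the four `tpVF` names of the VF rows, in the same data file. Their derivation footnotes are separate (68–71 against 64–67) and not visible.

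**The case against.** The strongest case is that these are clerical slips that a careful programmer would notice, in tables that SAP 5.3 makes exploratory.

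- **Upgrade patients also have a previous device**, and the inclusion criterion names upgrade and exchange together, so the sponsor may have wanted upgrades in the table. That could support including both groups. Nothing supports upgrades alone.
- **The electronic case report form is not visible.** If it also opens the question for upgrades, the table would not be empty. That part stands, but exchange patients would still be left out.
- **Comfort evidence is not all lost.** Investigators also rate size and shape for the patient's comfort against predecessor and competitor devices, with no such filter. This is true, but it does not replace the patient's own answer.
- **The RV and `tpVF` names differ from the expected ones by one letter**, and the text was read from PDF, where other variable names are visibly inconsistent. This doubt stands and is why the names must be confirmed in the data export. Against it, both odd RV entries are exactly the RA names.
- **The missing `Not done` note is editorial**, because SAP 9.2.6 already states the rule and SAP 5.1 bases frequencies on non-missing data. Agreed; it is listed only as a clean-up.

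Reliance on the programmer is also weaker than it sounds: the quality control required by SAP 1.2 covers endpoint analyses, and the wearing-comfort, RV and valve tables are not endpoints.

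**Conclusion.** The point holds and is minor. The wearing-comfort filter contradicts its own heading and every protocol statement of who is asked, and as written it admits 0 exchange patients. That rests only on upgrade and exchange being separate `PRIMTYP` levels, as SAP 8.2.1 shows. The expectation of few or no answers further assumes that sites follow Protocol 9.5 item 14.

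The RV finding (2 of 4 rows) assumes that the variable names were read correctly. For the valve note, 1 of 6 rows is certain to be wrong; the other 5 are affected only if the note spans them, which the PDF text does not settle. The two clean-ups have no shown numerical effect. Nothing here touches the primary endpoint, its test, the sample size, the significance level or the power.

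**What to change.** - **Wearing comfort, SAP 8.2.2:** change the filter to `PRIMTYP` = Device exchange.
- **RV table, SAP 8.2.5:** use `DURVSARE` and the RV pacing-adequacy item, after confirming both names in the data export.
- **Valve rows, SAP 8.2.1:** filter on `MHVHD` = Yes.
- **Clean-ups:** repeat in SAP 13.2 that `Not done` counts as missing for `DURVLVAS`, and give the four VT shock variables `tpVT` names, as the ATP and therapy tables do.

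The cost is a short SAP erratum, which Protocol 11.8 allows before the database is frozen or closed. If that point has passed, the affected tables can be re-run and the change reported as a deviation from the SAP. No new data are needed.

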8.2.3 AV delay optimization feature (AV Opt)

CIP chapter 8.1.4.5 AV delay optimization (for VR-T DX, DR-T, and Rivacor 5 HF-T and HF-T QP devices)

For all patients with VR-T DX or DR-T devices (only if clinically indicated), and for patients with Rivacor 5 triple-chamber devices (as Rivacor 5 is not equipped with CRT AutoAdapt) with sinus rhythm of sufficient intrinsic rate, the AV Opt test has to be performed during the PHD follow-up . Performance of the test during the 3-month follow-up is acceptable if it was not done at PHD.

AV Opt test / AV delay optimization

Data file, identifier patient_display_id_full	Notes	Variable name	Variable label	Variable level	nominal values
av_opt	descriptive with "Not done" to be analyzed as missing data	DUAVT	AV Opt test run	nominal	 Between Implantation and PHD  At PHD  At 3-month Follow-up  Not done
	descriptive	DUOAVT	Did the test suggest sensed and/or paced AV delay values?	nominal	 Yes  No

Data file, identifier patient_display_id_full	Notes	Variable name	Variable label	Variable level	nominal values
av_opt	descriptive for DUAVT=Not done	DUAVTND01	General lack of trust in automated test routines	nominal	 True  False
		DUAVTND02	Personal or institutional preference for use of alternative	nominal	 True  False
		DUAVTND03	Patient conditions prescribe AV delay settings without need for additional diagnostic aids	nominal	 True  False
		DUAVTND04	Atrial fibrillation	nominal	 True  False
		DUAVTND05	No sufficient intrinsic rate	nominal	 True  False
		DUAVTND10	Other	nominal	 True  False
		COAVTND	Please comment on reasons for not running AV Opt Test	text	n.a.

Data file, identifier patient_display_id_full	Notes	Variable name	Variable label	Variable level	nominal values
av_opt	descriptive	DUPCAVD	Suggested paced AV delay duration [ms]	scale	n.a.
	descriptive	DUSEAVD	Suggested sensed AV delay duration [ms]	scale	n.a.

AV Opt test / Final programmed AV delay settings

Data file, identifier patient_display_id_full	Notes	Variable name	Variable label	Variable level	nominal values
av_opt	descr.*	DUAVIDAP01	AV Delay after pace 01	scale	n.a.
	descr.*	DUAVIDAP02	AV Delay after pace 02	scale	n.a.
	descr.*	DUAVIDASE01	AV Delay after sense 01	scale	n.a.
	descr.*	DUAVIDASE02	AV Delay after sense 02	scale	n.a.
	descr.*	DUHRT01	AV Delay at rate 01	scale	n.a.
	descr.*	DUHRT02	AV Delay at rate 02	scale	n.a.
	descr.	DUAVIDCLA01	NEW: Do you consider the first suggested AV delay clinically acceptable?	nominal	 Yes  No
	descr.	DUAVIDCLA02	NEW: Do you consider the second suggested AV delay clinically acceptable?	nominal	 Yes  No
	descr.	DUAVIDTOUT	NEW: Final programmed AV delay settings based upon the AV Opt test output	nominal	 Yes  No
	descr.	DUAVIDPIP	Based upon the use of a personal/institutional preference	nominal	 Yes  No
	descr.	DUAVIDFUD	Based upon data from other follow-up affiliated diagnostics	nominal	 Yes  No
	descr.	DUAVIDSPR	Adoption of values from the device's standard program	nominal	 Yes  No
	descr.	DUAVIDIPR	Retention of AV delay settings from interrogated program	nominal	 Yes  No
	descr.	DUAVIDVPC	Long AV delay to avoid ventricular pacing	nominal	 Yes  No
	descr.	DUAVIDOTH	NEW: Other reason (please specify) for the final programmed AV delay settings	nominal	 Yes  No

Data file, identifier patient_display_id_full	Notes	Variable name	Variable label	Variable level	nominal values
av_opt	case listings for DUAVIDCLA01 = No	COAVDREA01	NEW: Reason for not considering first suggested AV delay acceptable	text	n.a.
	case listings for DUAVIDCLA02 = No	COAVDREA02	NEW: Reason for not considering second suggested AV delay acceptable	text	n.a.
	Case listing for DUAVIDOTH = Yes	COAVDOTH	NEW: Please specify other reason for the final programmed AV delay settings	text	n.a.

Data file, identifier patient_display_id_full	Notes	Variable name	Variable label	Variable level	Nominal values
av_opt	descriptive	DUAVOTAS	How do you rate the AV Opt tool?	nominal	 Very good  Good  Adequate  Poor  Very poor

Data file, identifier patient_display_id_full	Notes	Variable name	Variable label	Variable level	nominal values
av_opt	case listings for DUAVOTAS = Poor OR DUAVOTAS = Very poor	COAVOTAS	Please specify AV Opt tool rating	text	n.a.

